7.2.5 Sponsor Responsibility for Reporting Adverse Events

All Adverse Events will be reported to regulatory authorities, IRB/IECs and investigators in accordance with all applicable global laws and regulations, i.e., per ICH Topic E6 (R1) Guidelines for Good Clinical Practice.

7.3 TRIAL GOVERNANCE AND OVERSIGHT

7.3.1 Scientific Advisory Committee

This trial was developed in collaboration with a Scientific Advisory Committee (SAC). The SAC comprises both Sponsor and non-Sponsor scientific experts who provide input with respect to trial design, interpretation of trial results and subsequent peer-reviewed scientific publications.

7.3.2 Clinical Adjudication Committee

A Clinical Adjudication Committee (CAC) will evaluate the following events for the purposes of confirming them according to the criteria in Section 8.0 – Statistical Analysis Plan, as well as evaluating the presence of confounding factors.

ECIs pre-specified for adjudication are those that suggest potential intrusion of REM into either:

- 1) Wakefulness (ie, cataplexy or events suggestive of cataplexy) or,
- 2) Initiation of sleep (eg, sleep onset paralysis) or,

Falls/ataxia/worsening of balance will also be adjudicated to enhance data collection for these events, and to further evaluate whether an event might be due to cataplexy.

All personnel involved in the adjudication process will remain blinded to treatment allocation throughout the trial. Specific details regarding endpoint definitions can be found in the Adjudication Charter.

8.0 STATISTICAL ANALYSIS PLAN

This section outlines the statistical analysis strategy and procedures for the study. If, after the study has begun, but prior to any unblinding/final database lock, changes are made to primary and/or key secondary hypotheses, or the statistical methods related to those hypotheses, then the protocol will be amended (consistent with ICH Guideline E-9). Changes to exploratory or other non-confirmatory analyses made after the protocol has been finalized, but prior to unblinding/final database lock, will be documented in a supplemental Statistical Analysis Plan (sSAP) and referenced in the Clinical Study Report (CSR) for the study. Post hoc exploratory analyses will be clearly identified in the CSR. Separate analysis plans (ie, separate documents from the sSAP) will be developed to detail other planned analyses (ie, those specific to the analysis of PK data and pharmacogenomics analysis).

8.1 Statistical Analysis Plan Summary

All evaluations of suvorexant (with the exception of selected exploratory analyses) will be conducted without distinguishing the dose of suvorexant received (10 mg or 20 mg).

Key elements of the statistical analysis plan are summarized below; the comprehensive plan is provided in Section 8.2 through 8.12.

Study Design Overview	A Phase III Randomized, Placebo-Controlled Clinical Trial to Study the Safety and Efficacy of Suvorexant (MK-4305) for the Treatment of Insomnia in Subjects with Alzheimer’s Disease
Treatment Assignment	The study will be conducted as a double-blind study under in-house blinding procedures. Treatment allocation/randomization will occur centrally using an interactive voice response system (IVRS). Subjects will be assigned randomly in a 1:1 ratio to either suvorexant or placebo. The randomization will be stratified according to MMSE score (mild: 21 to 26, moderate: 12 to 20) assessed at the screening visit. Randomization will be monitored to ensure that approximately 30% of randomized subjects are in the moderate AD stratum.
Analysis Populations	Efficacy: Full Analysis Set (FAS) The FAS population is defined as randomized subjects who had: 1) at least 1 post-randomization observation for the analysis endpoint subsequent to at least 1 dose of trial medication and, 2) baseline data for those analyses that require baseline data. The number of subjects included in the FAS population may vary across endpoints due to the degree of missing data for each endpoint. Safety: All Subjects as Treated (ASaT) The ASaT population includes all subjects who took at least 1 dose of randomized trial medication. Subjects will be analyzed according to the treatment actually received.
Primary Endpoint(s)	PSG-derived Total Sleep Time (TST) in minutes, at Week 4.
Key Secondary Endpoints	PSG-derived Wakefulness After Sleep Onset (WASO) in minutes, at Week 4.
Statistical Methods for Key Efficacy Analyses	The primary hypothesis will be evaluated by comparing suvorexant and placebo with respect to change from baseline in PSG-derived total sleep time (TST) in minutes, at Week 4. Analysis of covariance (ANCOVA) using a general linear model for change from baseline in TST at Week 4, with terms for baseline TST value, baseline severity category (MMSE score of 12 to 20, 21 to 26), age category (non-elderly, elderly), gender, region, and treatment, will be used to evaluate the primary hypothesis. The significance of the difference between suvorexant and placebo in least squares means for change from baseline in TST will be evaluated using an appropriate contrast of model parameters, and according to the multiplicity testing strategy described below.
Statistical Methods for Key Safety Analyses	Program specific pre-specified adverse events of clinical interest (ECIs) will be assessed as Tier 1 events in this study. Estimates of the difference between treatments in the percentage of subjects with these events, 95% confidence intervals, and p-values, will be computed for these Tier 1 events. Tier 2 events are those events for which treatment differences and 95% confidence intervals (but not p-values) will be provided. Tier 3 safety parameters are those for which only descriptive statistics for treatment differences will be provided. Tier 1, 2 and 3

	safety parameters are summarized in Table 8 of Section 8.6.2, Statistical Methods for Safety Analysis.
Interim Analyses	No interim analysis for efficacy or safety is planned for this study.
Multiplicity	Statistical significance for the primary and secondary efficacy hypotheses will be based on a fixed sequential multiplicity strategy to control the overall Type I error at the two-sided 5% significance level. If the comparison of the primary endpoint between treatments is significant at the 5% significance level, then the comparison of the secondary endpoint between treatments will be evaluated at the 5% level of significance.
Sample Size and Power	
This study will randomize approximately 130 subjects into the suvorexant group and approximately 130 subjects into the placebo group, for a total of 260 randomized subjects in order to obtain 117 evaluable subjects per treatment group.
 
Power for the primary hypothesis
 
With approximately 130 subjects randomized per treatment group and assuming a standard deviation of 68 minutes for change from baseline in TST (based on insomnia subjects ≥ 65 years who had PSG in MK-4305 Protocols 028 and 029 pooled), a 2-sided $\alpha=0.05$, and a dropout rate of 10% at Week 4 (approximately twice the drop-out rate observed for insomnia subjects ≥ 65 years who had PSG in MK-4305 Protocols 028 and 029 pooled), the study has approximately 92% power to detect a true difference of 30 minutes between treatment groups with respect to change from baseline in TST at Week 4 (standardized effect size (SES) = 0.44); it has approximately 80% power to detect a 25-minute difference (SES = 0.37).

8.2 Responsibility for Analyses/In-House Blinding

The statistical analysis of the data obtained from this study will be the responsibility of the Clinical Biostatistics department of the Sponsor.

The study will be conducted as a double-blind study under in-house blinding procedures. The official, final database will not be unblinded until medical/scientific review has been performed, protocol violators have been identified, and data have been declared final and complete.

The Clinical Biostatistics department will generate the randomized allocation schedule(s) for trial medication assignment. Randomization will be implemented by an interactive voice response system (IVRS).

8.3 Hypotheses

Objectives and hypotheses of the study are stated in Section 3.

8.4 Analysis Endpoints

Key efficacy and safety endpoints that will be evaluated for within- and/or between-treatment differences are listed below, followed by the descriptions of the derivations of selected endpoints. Exploratory efficacy endpoints will be documented in the sSAP.

8.4.1 Efficacy and Ancillary Endpoints

Rationale for the key efficacy endpoints is given in Section 4.2.3.1 and an initial description of the efficacy measures is included in Section 7.1.2.2. In general, if a baseline value exists for a particular efficacy measure, then the change from baseline in that value will be evaluated. The primary efficacy evaluation period of this trial is the 1-month double-blind treatment period.

Primary Endpoint

The primary endpoint for this study is:

- total sleep time (TST) as measured in the sleep laboratory by PSG during an 8-hour recording period beginning at the subject's habitual bedtime, at Week 4 (minutes)

Secondary Endpoint

The secondary endpoint for this study is:

- wakefulness after persistent sleep onset (WASO) as measured in the sleep laboratory by PSG during an 8-hour recording period beginning at the subject's habitual bedtime, at Week 4 (minutes)

Exploratory Endpoints

The exploratory endpoints for this trial (eg other PSG parameters which further characterize the subject's sleep, treatment response based on achieving a clinically relevant predefined improvement in TST, sleep and activity parameters measured continuously during the trial by the activity/sleep watch, assessments of the subject's and trial partner's sleep, neuropsychiatric behavior inventory parameters and trial partner distress associated with the identified behaviors, high level assessments of the subject's mental state and performance, and trial medication titration history) will be detailed in the sSAP.

8.4.2 Safety Endpoints

An initial description of the safety measures is included in Sections 7.1.2.1, 7.1.2.2.10 and 7.1.3.

Safety and tolerability will be assessed by statistical and clinical review of the following data collected throughout the study: adverse experiences (AEs), laboratory values, ECGs, physical examinations, vital signs and treatment-emergent suicidality.

The Columbia-Suicide Severity Rating Scale (C-SSRS) will be used to systematically and prospectively ascertain and document the occurrence of suicidal events (ie, ideation and behavior). Responses on the C-SSRS are classified according to 11 pre-specified categories as described in Appendix 12.14.

The primary time period for safety analyses is the 1-month double-blind treatment period; safety summaries for the 14-day follow-up period (following the treatment period) will also be summarized.

Safety endpoints are classified into 3 tiers (see Statistical Methods for Key Safety Analyses in Section 8.1 for Tier definitions).

Tier 1 Safety Endpoints include the following program-specific pre-specified events of clinical interest (ECIs):

1. Suicidal ideation and/or behaviors
2. Events associated with potential for abuse
3. Complex sleep-related behaviors
4. Hypnagogic or hypnopompic hallucinations
5. Somnolence resulting in dose reduction or discontinuation of trial medication
6. Sleep paralysis and sleep-onset paralysis (adjudicated)
7. Cataplexy (adjudicated)
8. Falls/ataxia/worsening of balance (adjudicated to rule out cataplexy)
9. Agitation (daytime/nighttime)
10. Confusion or cognitive impairment (daytime/nighttime)

Tier 2 Safety Endpoints include (the proportion of subjects with):

1. Any AE
2. Any Serious AE
3. Any Drug-Related AE
4. Any Serious and Drug-Related AE
5. Discontinuation due to AE
6. Specific AEs, System Organ Class (SOC) AEs , and Predefined Limits of Change (PDLC) which have incidence of ≥ 4 subjects in 1 of the treatment groups

Tier 3 Safety Endpoints include:

1. Specific AEs, SOC AEs or PDLCs which have incidence < 4 subjects in all of the treatment groups
2. Change from baseline results for labs, ECGs and vital signs

In addition to the pre-specified ECI of suicidal ideation and/or behaviors based on AE reporting, which will be analyzed as a Tier 1 safety endpoint as described above, suicidal ideation and/or behaviors as reported on the C-SSRS will also be considered as a Tier 1 safety endpoint, in the event an investigator may determine for a given subject that suicidal

ideation reported on the C-SSRS is not in fact an adverse event. An analysis of this additional Tier 1 safety endpoint, based on positive responses on the C-SSRS rather than on AEs, will also be performed. Three pre-specified categories which summarize information reported on the C-SSRS (suicidal ideation, suicidal behaviors, and non-suicidal self-injurious behavior) and 5 pre-specified subcategories related to suicidal ideation and 5 pre-specified subcategories related to suicidal behaviors, as outlined in Appendix 12.14, will be considered as either Tier 2 or Tier 3 events (depending on the number of subjects with events observed during the assessment period). Counts for these pre-specified categories and subcategories will be analyzed according to the strategy outlined in Section 8.6.2, both with and without consideration of prior history of suicidal ideation and/or behaviors.

8.4.3 Derivations of Efficacy Endpoints

PSG Data

Sleep stage scoring of the PSG recordings will be performed for each 30-second epoch according to the 2007 American Academy of Sleep Medicine (AASM) scoring conventions by a central sleep scoring laboratory. Each 30-second epoch will be scored as wake, Stage N1, N2, N3 or R. For example, TST is defined as the sum of Stages N1+N2+N3+R (in minutes) and WASO is defined as the sum of all wake epochs beginning from persistent sleep (ie, the first epoch of 20 consecutive epochs of Stage N1, N2, N3 or R sleep) to lights on (in minutes). The primary and exploratory PSG endpoints for analysis will be derived by the central sleep scoring laboratory from this information according to pre-specified PSG endpoint definitions contained in a PSG endpoint definition document. The day range for PSG analysis endpoints is defined as follows: Week 4 (+/-7 days from the target Day 30).

8.4.4 Derivations of Safety Endpoints

Cataplexy and sleep-onset paralysis are defined as ECIs in this study which will be adjudicated by an independent, external CAC. Falls/ataxia/worsening of balance will also be evaluated as part of this adjudication process to rule out cataplexy. The adjudicated events will be evaluated as Tier 1 events as part of the tiered analysis strategy (see Section 8.6.2). Specific adverse experience terms relating to these ECIs will be identified and confirmed as part of the adjudication process prior to final study unblinding. Other Tier 1 events (eg, selected events associated with potential for abuse and complex sleep-related behaviors) that consist of multiple AE terms will be defined separately prior to unblinding.

Changes from baseline during the treatment period will be evaluated for laboratory, vital signs, and ECG data in accordance with predefined criteria noted Appendix 12.13.

8.5 Analysis Populations

8.5.1 Efficacy Analysis Populations

The Full Analysis Set (FAS) population will serve as the primary population for the analysis of efficacy data in this study. The FAS population consists of all randomized subjects who:

- Received at least 1 dose of trial medication,
- Have at least 1 post-randomization observation for the analysis endpoint subsequent to at least 1 dose of trial medication
- Have baseline data for those analyses that require baseline data

The number of subjects included in the FAS population may vary across endpoints due to the degree of missing data for each endpoint and the applicability of exclusion criteria to each endpoint (eg, need for baseline data only applies to those endpoints that are derived relative to baseline).

A supportive analysis using the Per-Protocol population will be performed for the primary and secondary efficacy endpoints. The Per-Protocol population excludes subjects due to important deviations from the protocol that may substantially affect the results of the primary and secondary efficacy endpoints. Potential violations that may result in the exclusion of a subject from the Per-Protocol population will be defined and determined and documented in a separate memo prior to the unblinding of the database.

Subjects will be included in the treatment group to which they were randomized for the analysis of efficacy data using both the FAS and Per-Protocol populations. Details on the approach to handling missing data are provided in Section 8.6.1 Statistical Methods for Efficacy Analysis.

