5.8 Subject Withdrawal/Discontinuation Criteria

Subjects may withdraw consent at any time for any reason or be dropped from the trial at the discretion of the investigator should any untoward effect occur. In addition, a subject may be withdrawn by the investigator or the Sponsor if enrollment into the trial is inappropriate, the trial plan is violated, or for administrative and/or other safety reasons. Specific details regarding discontinuation or withdrawal procedures; including specific details regarding withdrawal from Future Biomedical Research, are provided in Section 7.1.4 – Other Procedures.

[Table 4](#) provides reasons why a subject must be discontinued from treatment but may continue to be monitored in the trial, as well as reasons why a subject must be discontinued from treatment and the trial.

Table 4 Discontinuation Scenarios

Reason for Discontinuation Scenario	Action
The subject or legal representative (such as a parent or legal guardian) withdraws consent.	Discontinuation from Treatment and Trial
The subject's treatment assignment has been unblinded by the investigator, Merck subsidiary or through the emergency unblinding call center.	Discontinuation from Treatment, but Continue in Trial
The subject has a medical condition or personal circumstance which, in the opinion of the investigator and/or Sponsor, places the subject at unnecessary risk through continued participation in the trial or does not allow the subject to adhere to the requirements of the protocol.	Discontinuation from Treatment and Trial
The subject's trial partner is no longer willing (withdraws consent) or able to participate in the trial or is not compliant with trial-related procedures, and a suitable replacement trial partner cannot be identified within a reasonable period of time.	Discontinuation from Treatment and Trial
The subject is no longer able to participate in the trial or is not compliant with trial-related procedures.	Discontinuation from Treatment and Trial

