
The subject has an elevated ALT, AST, or T-BIL meeting any one of the following criteria:
 
 • ALT or AST $\geq 8x$ ULN; • ALT or AST $\geq 5x$ ULN for more than 2 weeks; • ALT or AST $\geq 3x$ ULN and T-BIL $\geq 2x$ ULN at the same visit; • ALT or AST $\geq 3x$ ULN with the appearance of symptoms indicating hepatitis (eg, worsening fatigue, nausea, vomiting, right upper quadrant pain or tenderness, fever, rash, or eosinophilia). 
Note: The Sponsor or its delegate should be immediately contacted when a subject is discontinued from trial medication or trial medication is interrupted because of an AE or a laboratory safety test abnormality.
	Discontinuation from Treatment, but Continue in Trial
The subject takes a prohibited medication during the trial.	This deviation should be documented, and the Sponsor should be consulted regarding the management of the subject.
Subjects who report suicidal ideation with intent, with or without a place or method (ie, a positive response to items 4 or 5 in the assessment of suicidal ideation on the C-SSRS) or suicidal behavior may meet discontinuation criteria.	Please refer to Section 7.1.2.2.11, 7.2.3.2 and the ECI guidance document for details.

Product: MK-4305
Protocol/Amendment No.: 061-01

Discontinuation from treatment is “permanent.” Once a subject is discontinued, he/she shall not be allowed to restart treatment.

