8.6.1 Statistical Methods for Efficacy Analysis

An analysis of covariance (ANCOVA) using a general linear model for change from baseline in TST at Week 4 with terms for baseline value, baseline severity category (MMSE score of 12 to 20, 21 to 26), age category (non-elderly, elderly), gender, region, and treatment, will be used to evaluate the primary hypothesis. The significance of the difference between suvorexant and placebo in least squares means for TST will be evaluated using an appropriate contrast of model parameters. Sensitivity analyses using this ANCOVA model in conjunction with multiple imputation (MI) to estimate the missing data and measurements collected following discontinuation of trial medication (if available) will also be performed. Details regarding the sensitivity analyses will be provided in the sSAP. The same ANCOVA model will be used to evaluate change from baseline in WASO at Week 4 according to the multiplicity testing strategy as described in Section 8.8. Statistical methods for the analysis of exploratory endpoints will be detailed in the sSAP.

Table 7 summarizes key efficacy analyses.

Table 7 Analysis Strategy for Key Efficacy Variables

Endpoint/Variable (Description, Timepoint)	Statistical Method	Analysis Population	Missing Data Approach
Primary:			
TST – Change from baseline at Week 4	ANCOVA†	Full Analysis set	Primary: Observed data
			Sensitivity: Multiple Imputation (Tipping Point)
Secondary:			
WASO – Change from baseline at Week 4	ANCOVA†	Full Analysis set	Primary: Observed data
			Sensitivity: Multiple Imputation (Tipping Point)
†ANCOVA model with terms for baseline value, baseline severity category (MMSE score of 12 to 20, 21 to 26), age category (nonelderly, elderly), gender, region, and treatment. ANCOVA = Analysis of Covariance Observed data = data observed during Treatment Phase which does not include data collected following discontinuation of trial medication			

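### As written, the MI/tipping-point sensitivity analysis for TST and WASO has no named population except a Full Analysis Set that leaves out subjects without a Visit 6 PSG

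*Combined protocol and SAP*

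**What the plan says.** Section 8.5.1 makes the FAS the primary efficacy population. Besides a dose of trial medication and, where needed, a baseline value, a member must "Have at least 1 post-randomization observation for the analysis endpoint subsequent to at least 1 dose of trial medication". Section 8.1 repeats the condition and adds: "The number of subjects included in the FAS population may vary across endpoints due to the degree of missing data for each endpoint". A missing endpoint therefore removes the subject from the set for that endpoint.

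Section 2.1 schedules three PSGs, two in screening and one at the end of treatment. The Trial Flow Chart (Section 6.0) marks PSG at Visits 2, 3 and 6 and has no PSG under Discontinuation.

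Table 7 in Section 8.6.1 names the FAS, and no other population, for both TST and WASO. The primary missing-data approach is observed data, defined as "data observed during Treatment Phase which does not include data collected following discontinuation of trial medication". The second line reads "Sensitivity: Multiple Imputation (Tipping Point)". The text of Section 8.6.1 describes the sensitivity work as the same ANCOVA with "multiple imputation (MI) to estimate the missing data and measurements collected following discontinuation of trial medication (if available)", and then: "Details regarding the sensitivity analyses will be provided in the sSAP".

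On who stays to Visit 6, Table 4 (Section 5.8) gives the action "Discontinuation from Treatment, but Continue in Trial" for unblinding and for the liver-test criteria. Consent withdrawal, medical or personal circumstance, loss of the trial partner, and the row "The subject is no longer able to participate in the trial or is not compliant with trial-related procedures" lead out of both treatment and trial. Section 7.1.5.3 lets subjects who stop medication remain in the trial and complete Visit 6.

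**The concern.** With one post-randomization measurement, requiring that measurement for entry to the analysis set excludes most of the subjects whose values are missing. A tipping-point analysis asks how bad the unseen outcomes would have to be to overturn the result. If subjects who left without a PSG are not in the set, their unseen outcomes are never varied. Any shift then acts only on those who returned off drug, and a smaller fraction of shifted subjects needs a larger shift to tip. The reported tipping point could look reassuring because few subjects were exposed to it.

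A related wording question decides whether even the returners are imputed. Section 8.6.1 can be read as using off-drug Visit 6 PSGs as collected, or as estimating those values by MI. On the first reading, MI within the FAS has essentially nothing to impute.

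**Working it through.** **Inputs.** From Section 8.9: 130 randomized per arm, 10% dropout, SD 68 minutes for TST change, two-sided alpha 0.05, effects of 30 and 25 minutes. The calculations use no covariates.

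**The plan's own figures.** 130 × 0.90 = 117 evaluable per arm. SE = 68 × √(2/117) = 8.89 minutes. Power at 30 minutes: Φ(30/8.89 − 1.960) = 92.1% (91.9% by the noncentral t). At 25 minutes: 80.3% (80.0%). The plan states 92% and 80%; both reproduce.

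**Subjects outside the set.** 130 − 117 = 13 per arm, 26 of 260. This is an upper figure, because some who stop drug may still attend Visit 6.

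**Significance limit.** With t(232) = 1.970, the observed difference must reach 1.970 × 8.89 = 17.52 minutes.

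**Tipping shift with all 13 suvorexant leavers imputed.** Lower their imputed values by d. The estimate falls by p·d and the shift adds variance, so d solves

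(obs − p·d) / √(2·68²/117 + p(1−p)d²/N) = 1.970, with p = 13/130 = 0.10 and N = 130.

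- Observed 20: d = 24.4 minutes
- Observed 25: d = 71.0 minutes
- Observed 30: d = 115.0 minutes

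Check for observed 30: (30 − 11.5)/√(79.0 + 9.2) = 18.5/9.39 = 1.970. Simulated MI with Rubin's rules gave z = 1.99, 1.97 and 1.97 at shifts of 24, 71 and 115.

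**Same formula inside the FAS.** Suppose r of the 13 suvorexant subjects return off drug and are imputed; then p = r/(117 + r) and N = 117 + r. The documents give no r, so this is an assumption with possible range 0 to 13. At r = 13 the answer equals the full set. At r = 6 the shifts are about 49, 138 and 218 minutes, roughly twice the full-set values. At r = 0 no tipping point exists.

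**Placebo-like change for suvorexant leavers.** The estimate becomes 0.9 × obs, so 20, 25 and 30 become 18.0, 22.5 and 27.0. Keeping the SE at 8.89, as Rubin's rules effectively do here, significance needs obs ≥ 17.52/0.9 ≈ 19.5. It is lost only for an observed 17.5 to 19.5 minutes. The chance of landing there is about 4% if the true effect is 30 minutes and 7% if it is 25.

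**Other dropout rates (assumptions), full set.** At 5%: about 57, 143 and 221 minutes. At 20%: about 7, 31 and 55 minutes.

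**The case against.** The best reply is that the analysis set for MI is a sensitivity detail, and those details are expressly left to the sSAP. That stands: the documents do not show that the trial lacks a suitable MI population, only that the protocol does not state one. Section 8.5.1 also calls the FAS the primary population, not the sole one. In Table 7 the sensitivity line carries no population entry of its own, so its link to the FAS is the natural reading rather than an explicit statement. No wider set is named anywhere, however, and a wider set in the sSAP would still have to be squared with Table 7.

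A reader might infer that MI within the FAS is self-contradictory or empty. The documents do not support that. Subjects who stop drug but complete Visit 6 under Section 7.1.5.3 meet the FAS condition, while their off-drug PSG is outside the observed data; they could be imputed. Nor does Table 4 predict how many leave, since subjects stopping for reasons it does not list may stay. If nobody were available to impute, the analyst would see it at once, so the misleading case is the intermediate one.

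The loss-of-significance range depends on the variance convention. Under a repeated-sampling SE, the estimate and its SE both shrink by 0.9, z is unchanged, and no significance is lost. The planned 10% dropout is also, by Section 8.9, about twice the rate seen in the earlier elderly PSG subjects.

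**Conclusion.** The point holds in a limited form. Followed literally, the protocol's only named set confines the MI/tipping-point analysis to subjects with a Visit 6 PSG and omits those who left without one, up to 13 per arm at 10% dropout. The check could then look stronger than it is.

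It would be wrong to infer that the primary result is compromised: the observed-data analysis, alpha, sample size and stated power are untouched. At the planned dropout, placebo-like outcomes for suvorexant leavers matter only for an observed difference of about 17.5 to 19.5 minutes, given SD 68, 117 completers per arm and Rubin's-rules variance. The shifts are illustrations for TST without covariates, not predictions. Severity is minor to moderate and confidence medium, because the sSAP may already settle it.

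**What to change.** Before unblinding, amend Table 7, Section 8.6.1 and the sSAP, or confirm that the sSAP already says so and align Table 7 with it:

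- Define the MI/tipping-point population for TST and WASO as all randomized subjects with at least one dose and a baseline PSG, in their randomized arm, whether or not a Visit 6 PSG exists.
- State whether off-drug Visit 6 PSGs are used as observed or imputed.
- Report the number imputed per arm.
- Keep the FAS for the observed-data primary analysis.

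The cost is a few lines of text and a little more analysis work, with no new data, visits or subjects. The reported tipping shift may come out smaller.
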